### 6.6.3. Mean Glucose and Glucose Management Indicator

The average glucose within a time period (a 24-hour period, daytime or nighttime) for each valid CGM day will be calculated first and then the average of daily average for a CGM session will be used as the mean glucose of the CGM session in the analysis.

The glucose management indicator (GMI) is a new parameter estimating A1c from CGM. The GMI is based on the above mean glucose (24-hour period) by CGM using the below formula (Bergenstal et al. 2018):

$$GMI(\%) = 3.31 + 0.02392 \times \text{mean glucose (mg/dL)}$$

### 6.6.4. Glycemic Variability

Glycemic variability will be derived using the notation below:

*i* represents a time point within a time period (a 24-hour period, daytime or nighttime).

*n* represents the number of time points within the time period.

*k* represents a valid CGM day within a visit.

*m* represents the number of valid CGM days in the specific time period at a visit.

$BG_{k,i}$  represents the glucose value at time point *i* on day *k* unless otherwise specified.

Sections 6.6.4.1 and 6.6.4.2 provide the derivation method for variables assessing within-day and between-day glucose variability based on CGM readings.

#### 6.6.4.1. Within-Day Variability

For variables assessing within-day variability, first determine the variability within each valid CGM day, then average across days within a CGM session.

Within-day glucose SD (Rodbard 2009):

$$SD = \frac{1}{m} \sum_{k=1}^m SD_k = \frac{1}{m} \sum_{k=1}^m \sqrt{\frac{\sum_{i=1}^n (BG_{k,i} - \bar{BG}_{k,i})^2}{n-1}}$$

Within-day glucose CV (Clarke and Kovatchev 2009):

$$CV = \frac{1}{m} \sum_{k=1}^m CV_k = \frac{1}{m} \sum_{k=1}^m \frac{SD_k}{\left( \frac{\sum_{i=1}^n BG_{k,i}}{n} \right)} \times 100$$

The low blood glucose index (LBGI), high blood glucose index (HBGI), and blood glucose risk index (BGRI) will be calculated using the following standard formulas (Kovatchev et al. 2006).

The LBGI, HBGI, and BGRI will be derived for each valid CGM day of a visit and then average across days within a CGM session. The calculations of LBGI, HBGI, and BGRI take the following steps:

1. For each blood glucose (BG [mg/dL]) at the  $i^{\text{th}}$  time point, compute the following:

$$f(BG_i) = 1.509 \times [(\ln(BG_i))^{1.084} - 5.381]$$

2. Compute BG risk for each reading

$$rl(BG_i) = 10 \times f(BG_i), \text{ if } f(BG_i) < 0; \text{ otherwise } rl(BG_i) = 0$$

$$rh(BG_i) = 10 \times f(BG_i), \text{ if } f(BG_i) > 0; \text{ otherwise } rh(BG_i) = 0$$

3. Compute LBGI and HBGI

$$LBGI = \frac{1}{n} \sum_{i=1}^n rl(BG_i)$$

$$HBGI = \frac{1}{n} \sum_{i=1}^n rh(BG_i)$$

4. Compute BGRI

$$BGRI = LBGI + HBGI$$

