## 10.9. Appendix 9: Abbreviations and Definitions

Term	Definition
abuse	Use of a study intervention for recreational purposes or to maintain an addiction or dependence
ADA	anti-drug antibody
AE	adverse event
ALP	alkaline phosphatase
ALT	alanine aminotransferase
ANCOVA	analysis of covariance
AST	aspartate aminotransferase
BG	blood glucose
blinding	A single-blind study is one in which the investigator and/or the investigator's staff are aware of the treatment but the participant is not, or vice versa, or when the sponsor is aware of the treatment but the investigator and/or the investigator's staff and the participant are not.
	A double-blind study is one in which neither the participant nor any of the investigator or sponsor staff who are involved in the treatment or clinical evaluation of the subjects are aware of the treatment received.
CGM	continuous glucose monitoring: can refer to study procedure or analysis of representative CGM derived variables including but not limited to:
	
 
• Time in Range
 
• Time Below Range
 
• Time Above Range
 
• Daily Average Glucose
 
• Glucose Management Indicator
 
• Between- and Within-Day Glucose Variability
 
• Low Blood Glucose Index; High Blood Glucose Index; Blood Glucose Risk Indicator
 
• Ambulatory Glucose Profiles with interquartile ranges
 

CI	confidence interval
CIOMS	Council for International Organizations of Medical Sciences
Companion diagnostic	An in vitro diagnostic device (assay or test) that provides information that is essential for the safe and effective use of a corresponding therapeutic product
complaint	A complaint is any written, electronic, or oral communication that alleges deficiencies related to the identity, quality, purity, durability, reliability, safety or effectiveness, or performance of a drug or drug delivery system.

compliance	Adherence to all study-related, good clinical practice (GCP), and applicable regulatory requirements.
CRF	case report form; a printed, optical, or electronic document designed to record all of the protocol-required information to be reported to the sponsor for each trial participant.

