For categorical measures, summary statistics will include sample size, frequency, and percentages. Fisher's exact test or logistic regression will be used for treatment comparisons, unless otherwise stated.

For laboratory values, both conventional (CN) and System International (SI) units will be presented. Therefore, both % and mmol/mol will be presented for HbA1c and both mg/dL and mmol/L will be presented for glucose measurements.

In this study, the negative binomial regression will be used to analyze the number of hypoglycemic episodes. Group Mean instead of LS mean will be estimated and delta method will be used to estimate the standard error of the Group Mean (Qu and Luo 2015). Group Mean is defined as the mean response in the treatment group for the studied population. The difference between LS mean and the Group Mean is that LS mean estimates the response by taking the inverse link function on mean covariates, while the Group Mean takes the inverse link function on individual patient covariates first and then averages over all patients. For severe

hypoglycemia, the empirical method based on exposure adjusted rate (calculated by total number of events divided by total exposure) may be used for the treatment comparison if the number of episodes is too small and leads to convergency issues in the negative binomial regression model.

The table below describes the definition of baseline and post-baseline observations for different analyses.

Analysis	Baseline Observations	Post-Baseline Observations
HbA1c (treatment regimen estimand)	The baseline is the last non-missing assessment prior to or on the day of the first dose of study treatment (CRF is used to determine).	Planned measurements at Week 26 (primary endpoint, Visit 23) in EAS1. Use unplanned measurements if no planned measurement.  Multiple imputation approach will be used to impute missing observations at Week 26 (Visit 23).
HbA1c (efficacy estimand)	The baseline is the last non-missing assessment prior to or on the day of the first dose of study treatment.	Weeks 2, 4, 12, 16 and 26 (Visit 5, 7, 15, 17 and 23) in EAS2 for MMRM.  Planned measurements at scheduled visits will be included. Use unplanned measurements if no planned measurement

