Event rate of Level 1 hypoglycemic events (events/participant/year): • All documented	Baseline, 0-6, 0-12, 0-26, 12-26 weeks, post-treatment period	Negative binomial regression with treatment, baseline HbA1c and baseline Level 1 hypoglycemia rate as covariates, log (exposure/365.25 days) as the offset in the model.
Event rate of Level 2 hypoglycemic events (events/participant/year): • All documented	Baseline, 0-6, 0-12, 0-26, 12-26 weeks, post-treatment period	Negative binomial regression with treatment, baseline HbA1c and baseline Level 2 hypoglycemia rate as covariates, log (exposure/365.25 days) as the offset in the model.

Endpoint	Analysis Period	Statistical Method
Event rate of Level 3 hypoglycemic events (events/participant/year): 
 
• All documented
 
	Baseline, 0-26 weeks, post-treatment period	Negative binomial regression with treatment, baseline Level 3 hypoglycemia rate and baseline HbA1c as covariates, log (exposure/365.25 days) as the offset in the model.  If the number of events is too small to run the negative binomial regression, exposure adjusted rate calculated by total number of events divided by total exposure for individual patients) will be provided and the empirical method (see Appendix 11 (Section 6.11) for details) will be used for treatment comparison.
Event rate of Level 2/3 hypoglycemic events (events/participant/year): 
 
• All documented
 
• Nocturnal
 
• Non-nocturnal
 
	Baseline, 0-6, 0-12, 0-26, 12-26 weeks, post-treatment period	Negative binomial regression with treatment, baseline HbA1c and baseline hypoglycemia rate of the same hypoglycemia type as covariates, log (exposure/365.25 days) as the offset in the model.  The plots of the mean cumulative functions (MCFs) by each treatment arm will also be created. The population mean for cumulative number of events up to time t, $M(t)$ , will be estimated using a nonparametric estimation method described by Nelson (2003).
Incidence of Level 1 hypoglycemic events: 
 
• All documented
 
	Baseline, 0-6, 0-12, 0-26, 12-26 weeks, post-treatment period	Logistic regression with treatment, baseline HbA1c and baseline Level 1 hypoglycemia incidence as covariates.

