$$\left[ \hat{\lambda} \exp\left(-z_{1-\frac{\alpha}{2}} \sqrt{\widehat{Var}(\log(\hat{\lambda}))}\right), \quad \hat{\lambda} \exp\left(z_{1-\frac{\alpha}{2}} \sqrt{\widehat{Var}(\log(\hat{\lambda}))}\right) \right] \quad (1)$$

The p-value for testing the null hypothesis of  $H_0: \lambda = 1$  is calculated as

$$p = 2\Phi\left(\left|\log(\hat{\lambda})\right|/\sqrt{\widehat{Var}(\log(\hat{\lambda}))}\right) \quad (2)$$

The missing values will be imputed using multiple imputation by the retrieved dropout approach. The retrieved dropout participants are those who discontinue study intervention prior to Week 26 but have non-missing measures at Week 26. If there are only a limited number of retrieved participants that leads to a failure in performing the multiple imputation analysis, such as the model cannot converge, or the number of retrieved dropout participants is small, the missing HbA1c at Week 26 will be imputed by return-to-baseline multiple imputations.

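### Two SAP formulas are wrong as printed: LBGI can never be positive, so lows cancel highs in BGRI, and the fallback p-value for the Level 3 event rate lies between 1 and 2

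*SAP*

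**What the plan says.** **LBGI, HBGI and BGRI (SAP 6.6.4.1).** The SAP says these indices "will be calculated using the following standard formulas", with a literature citation.

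- Step 1 transforms each reading: "f(BG_i) = 1.509 \times [(\ln(BG_i))^{1.084} - 5.381" (closing bracket follows).
- Step 2 sets the low-glucose risk: "rl(BG_i) = 10 \times f(BG_i), \text{ if } f(BG_i) < 0", otherwise 0. The high-glucose risk rh uses the same expression when f is above 0.
- Step 3 averages rl into LBGI and rh into HBGI.
- Step 4 sets "BGRI = LBGI + HBGI".

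Protocol Appendix 9 (10.9) includes "Low Blood Glucose Index; High Blood Glucose Index; Blood Glucose Risk Indicator" among its examples of CGM-derived variables. The SAP derives them under glycemic variability, which is an other secondary endpoint.

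**Fallback p-value (SAP 6.11, Appendix 11).** Equation (2) begins "p = 2\Phi\left(\left|\log(\hat{\lambda" and goes on to divide the absolute log relative rate by its standard error inside Φ. It tests the null hypothesis that the relative rate is 1. The method serves the Level 3 event rate. Section 4.1 says it "may be used for the treatment comparison if the number of episodes is too small", and the table in Section 4.6.2.2.1 opens the condition with "If the number of events is too small to run the negative binomial regression".

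**The concern.** A low-glucose risk should be non-negative and should grow as glucose falls. The printed rl does the opposite: it is zero or negative, and more negative the deeper the low. Adding it to HBGI makes hypoglycemia pay for hyperglycemia. Programmed literally, the arm with more low readings can show the better BGRI, in a trial that compares two basal insulins partly on hypoglycemia.

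Equation (2) applies the normal distribution function to a quantity that is never negative, so the result cannot fall below 1 and rises as the evidence strengthens. It disagrees with interval (1) printed just above it, which is correctly formed. Use of the fallback is plausible: exclusion criterion 16 removes people with severe hypoglycemia in the 6 months before screening, so Level 3 events may be few, and the SAP itself plans for that case.

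**Working it through.** The SAP gives no worked value for either formula, so there is no stated figure to reproduce. The formulas were evaluated exactly as printed. The glucose profiles and event counts below are assumed illustrations.

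**1. LBGI and BGRI**

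Input: f(BG) = 1.509 × [(ln BG)^1.084 − 5.381], BG in mg/dL. It is zero at BG = exp(5.381^(1/1.084)) = 112.5.

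| BG (mg/dL) | f | rl as printed | rh as printed |
|---|---|---|---|
| 40 | −1.91 | −19.1 | 0 |
| 50 | −1.50 | −15.0 | 0 |
| 54 | −1.36 | −13.6 | 0 |
| 70 | −0.88 | −8.8 | 0 |
| 150 | +0.54 | 0 | 5.4 |
| 250 | +1.50 | 0 | 15.0 |

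Every rl is zero or negative, so LBGI ≤ 0. Because rl + rh = 10 × f for every reading, BGRI is the mean of 10 × f.

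Half the readings at 50 and half at 250 mg/dL: LBGI = 0.5 × (−15.0) = −7.50; HBGI = 0.5 × 14.98 = 7.49; BGRI = −0.01. A flat day at 112.5 mg/dL also gives about 0.

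Flat day at 150 mg/dL with a share q of readings moved to 50 mg/dL: BGRI = (1 − q) × 5.37 + q × (−15.00).

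| q | BGRI as printed |
|---|---|
| 0% | 5.37 |
| 5% | 4.35 |
| 10% | 3.33 |
| 20% | 1.30 |

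The index improves as lows are added.

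Two possible repairs, both assumed because the documents do not reproduce the cited formula, applied to the half-50/half-250 day:

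- 10 × |f|: LBGI 7.50, HBGI 7.49, BGRI 14.99.
- 10 × f² in both lines: LBGI 11.25, HBGI 11.22, BGRI 22.47.

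Either makes LBGI non-negative and stops the cancellation. They are not interchangeable: squaring also changes HBGI, and a sign change does not.

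**2. Equation (2)**

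Write z = |log λ|/SE.

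| z | 2Φ(z), printed | 2[1 − Φ(z)] |
|---|---|---|
| 0 | 1.000 | 1.000 |
| 1 | 1.683 | 0.317 |
| 1.96 | 1.950 | 0.050 |
| 3 | 1.997 | 0.003 |

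The printed values start at 1 and approach 2.

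Illustration with Appendix 11's own variance (assumed: 335 per arm, equal exposure, 15 events versus 5, each in a different participant):

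- λ = 15/5 = 3.0, log λ = 1.099.
- With 0/1 counts, S² = (Y − Y²/n)/(n − 1): 0.0147 for Y = 5 and 0.0429 for Y = 15.
- Var(log λ) = 335 × 0.0147/5² + 335 × 0.0429/15² = 0.198 + 0.064 = 0.261, so SE = 0.511.
- Interval (1): 3.0 × exp(±1.96 × 0.511) = 1.10 to 8.17, which excludes 1.
- z = 1.099/0.511 = 2.15. Equation (2) gives p = 1.97; the corrected form gives p = 0.032.

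**The case against.** The case for treating this as editorial has five parts.

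- **Extraction.** The text was read from PDF by a program, and a lost sign or exponent could explain either formula. This stands as a reason to check the PDF first. It does not dispose of the point: the 1.084 exponent, the squares in the SD formulas, the −2 powers in Appendix 11 and the minus sign in interval (1) all survived. If f was meant to be squared, the square would have to be missing from both the rl and rh lines.
- **Visibility.** A p-value of 1 or more cannot be mistaken for a result, cannot give a false positive, and would probably be caught in programming. That is fair for equation (2). It is weaker for BGRI, where cancellation gives small, plausible numbers.
- **LBGI alone still ranks correctly.** If only the sign is wrong, the LBGI contrast keeps its size with its direction reversed. True; the loss of information is in BGRI.
- **Reach.** The protocol mention is a glossary entry, and no objectives table names the three indices. They enter through the general glucose variability endpoint, which is not multiplicity-adjusted. Equation (2) is a conditional fallback for a tertiary safety endpoint. Hypoglycemia is also measured directly by time below range, CGM episodes and diary events. All of this is correct and limits the severity.
- **A citation governs.** A programmer could follow the cited source. But the SAP prints explicit steps as that source's formulas, and nothing elsewhere in the SAP corrects them.

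**Conclusion.** The point holds by arithmetic on the printed formulas, without any outside source. As written, LBGI ≤ 0, BGRI lets low readings offset high ones, and equation (2) returns values from 1 up to, but not reaching, 2. These are stated analysis rules that give wrong results if followed.

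The reach is limited. The empirical confidence interval, the Level 3 incidence analysis, the SD, CV and MODD variability measures, CGM time below range, CGM hypoglycemia episodes, and all primary and key secondary analyses are unaffected. The correction should be made, but it does not threaten the trial's main conclusions.

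Confidence is medium, because the conclusion assumes the formulas were extracted faithfully. The worked profiles and the 15-versus-5 split show how the formulas behave; they do not predict an effect in this trial.

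**What to change.** 1. Compare both formulas with the original PDF.
2. If confirmed, correct step 2 of SAP 6.6.4.1 so that the low-glucose risk is non-negative and rises as glucose falls. Take the exact form from the source the SAP cites, use the same form in the rl and rh lines, and check the derivation programs against it. The documents do not settle whether |f| or f² is intended.
3. Replace equation (2) in Appendix 11 with p = 2[1 − Φ(|log λ|/SE)], which agrees with interval (1), and check the program.

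The cost is two formula corrections in the SAP appendices and a program check. No new data are needed, and the design, alpha, and primary and key secondary analyses do not change.

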**6.6.4.2. Between-Day Variability**

For variables assessing between-day variability, first determine the variability for each time point across days within a CGM session then average across all time points.

Between-day glucose SD (Rodbard 2009):

$$SD = \frac{1}{n} \sum_{i=1}^n SD_i = \frac{1}{n} \sum_{i=1}^n \sqrt{\frac{\sum_{k=1}^m (BG_{k,i} - \left\{ \frac{\sum_{k=1}^m BG_{k,i}}{m} \right\})^2}{m-1}}$$

Between-day glucose CV (Kovatchev et al. 2009):

$$CV = \frac{1}{n} \sum_{i=1}^n CV_i = \frac{1}{n} \sum_{i=1}^n \left( \frac{SD_i}{\frac{\sum_{k=1}^m BG_{k,i}}{m}} \right) \times 100$$

Mean of daily differences (MODD): this parameter is calculated as the mean of absolute differences between glucose values at corresponding time points of consecutive days.

$$MODD = \frac{1}{m-1} \sum_{k=1}^{m-1} \frac{\sum_{i=1}^n |BG_{k+1,i} - BG_{k,i}|}{n}$$

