## 1.1. Objectives, Endpoints, and Estimands

Objectives	Endpoints
Primary	
Demonstrate noninferiority of LY3209590 compared to insulin glargine on glycemic control.	Change in HbA1c from baseline at Week 26
Key Secondary (Multiplicity Adjusted)	
Demonstrate LY3209590 is superior to insulin glargine in the selected parameters of glycemic control.	
 
Change in HbA1c from baseline at Week 26
 
The percentage of participants achieving HbA1c <7% at Week 26 without nocturnal hypoglycemia (<54 mg/dL [3.0 mmol/L] or severe) during treatment phase up to Week 26
 
The event rate of participant-reported clinically significant nocturnal hypoglycemia (<54 mg/dL [3.0 mmol/L] or severe) during treatment phase up to Week 26
 

Other Secondary	
To investigate the effect of LY3209590 compared with insulin glargine in additional parameters of diabetes management.	
 
Change in fasting glucose measured by SMBG from baseline to Week 26
 
Time in glucose range between 70 and 180 mg/dL (3.9 and 10.0 mmol/L), inclusive measured during the CGM session that occurs between Week 22 and Week 26
 
Time in hypoglycemia range with glucose <54 mg/dL (3.0 mmol/L), measured by CGM that occurs between Week 22 and Week 26
 
Time in hyperglycemia range with glucose >180 mg/dL (10.0 mmol/L), measured by CGM that occurs between Week 22 and Week 26
 
Glucose variability measured during the CGM session that occurs between Week 22 and Week 26
 
Insulin dose at Week 26 
 
basal
 
bolus
 
total, and
 
basal/total insulin dose ratio
 
 
 

To investigate the safety of LY3209590 compared with insulin glargine.	
 
Incidence and rate of composite of Level 2 and 3 hypoglycemia events during treatment period
 
Body weight change from baseline to Week 26
 

To investigate the treatment impact of LY3209590 compared with insulin glargine on patient-reported outcome measures.	
 
Treatment experience at Weeks 26 for DID-EQ
 

Tertiary	

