#### 4.4.2. Supportive Secondary Endpoints

##### 4.4.2.1. Other Efficacy Endpoints

The analyses for CGM variability parameters, insulin dose and patient reported outcomes will be based on the efficacy estimand using EAS2 data.

The analysis of CGM data (except for variability parameters) and fasting glucose from SMBG will be done for both treatment regimen estimand and efficacy estimand. Analysis of covariance for treatment regimen estimand and MMRM model for efficacy estimand similar to those for the primary endpoint with an additional term of baseline HbA1c stratum ( $<8.0\%$ ,  $\geq 8.0\%$ ) will be used.

The variance-covariance structure in the MMRM models for fasting glucose from SMBG and insulin dose will be based on compound symmetry.

For treatment regimen estimand, only subjects with an observation at baseline or at Week 26 (Visit 23) will be included in the analysis. The missing baseline will be imputed using multiple imputation with assumption of missing at random. Missing data at Week 26 (Visit 23) will be imputed as described for the primary HbA1c endpoint.

For the efficacy estimand, only participants with baseline and at least one post baseline observation will be included in the analysis, missing data will be handled by MMRM model.

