## 6.6. Appendix 6: Derivation of CGM Variables

Blinded CGM will be worn by participants at the following designated weeks:

- Two weeks in screening/lead-in period with the data download at Week 0 (Visit 3)
- Four weeks after the initiation of study treatment with the data download at Week 4 (Visit 7)
- Four weeks near the end of weekly titration period with the data download at Week 12 (Visit 15)
- Four weeks near the primary endpoint with the data download at Week 26 (Visit 23)
- Four weeks after the end of study treatment period with the data download at Week 31 (Visit 802).

Linear interpolation will be used to impute the missing glucose readings during intervals  $>7$  minutes and  $\leq 15$  minutes. Missing data will be imputed at a 5-minute interval using the BG value before and the one after the interval. For example, the BG reading before the interval is 50 mg/dL at time 100 min, and the BG reading after interval is 70 at time 115 min, then the missing records will be imputed as:

- at time 105 min, BG reading= $50+5*(70-50)/(115-100)=56.7$ ,
- at time 110 min, BG reading= $50+10*(70-50)/(115-100)=63.3$

Glucose reading intervals  $>15$  minutes will be treated as missing data and not be counted in the length of the analysis periods.

For the primary analysis, CGM data must meet minimal completeness criteria for the period and the session in order to be included as a valid time period and session.

As shown in the table below, all the CGM derivations are based on the data from valid CGM periods of a day and sessions unless otherwise specified.

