### Minimum Data Available to Define a Valid Period of the Day and CGM Session

Period	Definition	Minimum Valid CGM Time Period for a Session
Valid CGM Day (00:00-23:59)	$\geq 70\%$ of expected values available ( $\geq 202$ of 288 values)	3 valid CGM days define a CGM session for 24-hour

Valid CGM Nighttime (00:00-05:59)	$\geq 70\%$ of expected values available ( $\geq 50$ of 72 values)	3 valid CGM days define a CGM session for Nighttime
Valid CGM Daytime (06:00-23:59)	$\geq 70\%$ of expected values available (151 of 216 values)	3 valid CGM days define a CGM session for Daytime

Sensitivity analysis will be done for selected parameters including all CGM data.

The ambulatory glucose profile during the 24-hour period will be generated with interquartile ranges, at treatment-group level by CGM session, based upon the observed and imputed CGM measures.

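### The MODD formula in the SAP pairs successive valid CGM days, so across an invalid day it differences days that are not consecutive, contrary to its definition in words

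*SAP*

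**What the plan says.** SAP Section 6.6.4.2 describes MODD in words: "this parameter is calculated as the mean of absolute differences between glucose values at corresponding time points of consecutive days". It then prints a formula that takes the mean absolute difference between day k and day k+1 over the n time points, sums this from k = 1 to m−1, and divides by m−1.

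The notation is set one level up, in Section 6.6.4. There k "represents a valid CGM day within a visit", and m "represents the number of valid CGM days in the specific time period at a visit". Appendix 6 (Section 6.6) adds that "all the CGM derivations are based on the data from valid CGM periods of a day and sessions unless otherwise specified". A day therefore has to reach 70% of its expected readings before it enters the index at all.

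The completeness table in the same appendix sets the floor for a session: "3 valid CGM days define a CGM session for 24-hour", with the same count of three for nighttime and for daytime. It does not ask that the three days be adjacent. The session before Visit 23 lasts four weeks.

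MODD falls under an other secondary endpoint in SAP Section 1.1: "Glucose variability measured during the CGM session that occurs between Week 22 and Week 26". Section 4.4.2.1 places it on one estimand: "The analyses for CGM variability parameters, insulin dose and patient reported outcomes will be based on the efficacy estimand using EAS2 data".

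**The concern.** The words and the formula agree only if every day between the first and last valid day of a session is itself valid. An invalid day has no index value, so the days on either side of it become k and k+1. If days 3 and 4 fail the 70% rule, day 2 is differenced against day 5, and that difference counts in full. Nothing in Section 6.6 drops or flags such a pair.

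Two programmers could therefore derive different values from the same section, one following the sentence and the other the formula. Under the formula, the reported figure also mixes one-day differences with longer ones, in a proportion set by how much data a participant lost. At the extreme, a session with valid days 1, 10 and 20 meets the three-day minimum and gets a MODD without containing a single day-to-day difference.

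**Working it through.** The documents give no numerical value for MODD, so there is no figure to reproduce. The check applies the printed formula and compares it with the same mean restricted to pairs exactly one calendar day apart.

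**Inputs from the SAP.** k and m run over valid days (6.6.4); the divisor is m−1 (6.6.4.2); three valid days make a session (Appendix 6 table); the endpoint session lasts four weeks, taken as 28 days (Appendix 6).

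**Step 1: a sparse session by hand.** Take valid days 1, 2 and 5 and assume that glucose drifts by 5 mg/dL per day at every time point.
- Printed formula: pairs (1,2) and (2,5) differ by 5 and 15; (5 + 15)/2 = 10.0.
- Adjacent days only: pair (1,2); 5/1 = 5.0.

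The printed value is double.

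**Step 2: direction.** Assume a pure seven-day sawtooth of 40 mg/dL peak to trough and nothing else. The mean absolute difference by gap is then:

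| Gap (days) | 1 | 2 | 3 | 4 | 5 | 6 | 7 |
|---|---|---|---|---|---|---|---|
| mg/dL | 11.4 | 19.0 | 22.9 | 22.9 | 19.0 | 11.4 | 0 |

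Gaps of two to five days raise MODD, a six-day gap leaves it unchanged, and a seven-day gap lowers it to zero. With a flat profile and independent days, the gap makes no difference in expectation.

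**Step 3: well-filled sessions, quick calculation.** Assume 20% of days invalid at random, so about 20% of successive valid pairs are not adjacent. Assume also a day-to-day correlation of 0.3 that decays geometrically, with no other noise. The expected absolute difference scales with √(1−ρ).
- One-day gap: √0.70 = 0.837. Two-day gap: √(1−0.09) = √0.91 = 0.954. Ratio 0.954/0.837 = 1.14.
- 20% of pairs × 14% ≈ 3%.

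**Step 4: well-filled sessions, simulation.** Assumed values: 600 participants per scenario, 28-day sessions, 48 time points per day, day-level SD 15 mg/dL, residual SD 15 mg/dL, scattered invalid days. Entries are the printed formula divided by the adjacent-day version; ratios just below 1 are simulation noise.

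| Invalid days | Flat, correlation 0 | Flat, correlation 0.5 | Weekly 20 mg/dL, correlation 0 | Weekly 40 mg/dL, correlation 0 | Weekly 40 mg/dL, correlation 0.5 |
|---|---|---|---|---|---|
| 0% | 1.000 | 1.000 | 1.000 | 1.000 | 1.000 |
| 10% | 0.999 | 1.008 | 1.000 | 1.011 | 1.019 |
| 20% | 1.003 | 1.016 | 1.005 | 1.021 | 1.034 |
| 30% | 0.997 | 1.028 | 1.008 | 1.024 | 1.061 |

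With residual SD 25, or with invalid days in three-day blocks, no ratio exceeds 1.03.

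At 20% invalid days the range is about 0 to 3%. If one arm had the 40 mg/dL weekly pattern and the other a flat profile, both with correlation 0.5, the ratios would differ by 1.034 − 1.016 = 0.018 at 20% invalid days and by 1.061 − 1.028 = 0.033 at 30%.

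**The case against.** The best defence is that there is no contradiction. Section 6.6.4.2 says consecutive days, not consecutive calendar days. Section 6.6.4 has just defined a day k as a valid day, and Appendix 6 restricts all CGM derivations to valid periods. On that reading consecutive means next in the valid-day sequence, which is what the formula computes. The reading is possible, but the SAP does not state it. Where the appendix means valid days it usually says so, and the name of the measure points to day-to-day change. Between-day SD and CV already pool valid days at every separation, so adjacency is what MODD adds to them. If the sponsor does intend successive valid days, one added word would settle the matter.

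The second defence is size. Protocol Section 8.1.1.2 sets an 80% compliance threshold per session, with re-education and vendor review of uploads, so sparse sessions may be few. Section 6.6.4 yields several other variability measures, and SAP Section 1.1 does not name MODD. This stands, and it keeps the point minor.

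A reader might go further and infer that the formula inflates MODD in the LY3209590 arm, since days further apart also differ in time since a weekly dose. The SAP does summarize LY3209590 glucose by day 0 to 6 after dosing (Sections 4.4.2.1.1 and 6.6.1), so a within-week pattern is worth considering. But the documents give no within-week glucose amplitude and no share of invalid days by arm. Protocol Section 2.2 describes a low peak-to-trough ratio, which points towards a flat profile. The 3% in step 3 uses one correlation common to both arms and implies no difference between them. The between-arm gaps in step 4 come entirely from the assumed 40 mg/dL sawtooth; at 20 mg/dL the ratio is at most 1.01.

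**Conclusion.** The mismatch holds and can be read directly from Sections 6.6.4 and 6.6.4.2. The printed formula changes the value in any session with an invalid day between two valid ones, unless the differences happen to be equal.

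The effect is nil with no invalid days and probably small in well-populated sessions. It can be large in sparse ones, as the doubling in step 1 shows. All of these sizes rest on assumed correlations, noise, weekly amplitude and invalid-day share. The direction is not fixed, so inflation should not be claimed as a general result. A difference between the weekly and daily arms is possible, but the documents neither show nor quantify one.

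The endpoint lies outside the multiplicity-controlled family, so no primary or key secondary conclusion is affected. This is a derivation detail worth correcting before the data are programmed.

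**What to change.** In Section 6.6.4.2, sum only over pairs of valid days that are adjacent calendar days, divide by the number of such pairs instead of m−1, and set MODD to missing when a session has none. Apply the rule separately to the 24-hour, daytime and nighttime periods, since validity is defined for each.

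If the sponsor prefers to keep the printed formula, the sentence should say successive valid days, and the report should note that the measure then includes gaps longer than one day.

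The cost is one line in the derivation. A few sparse sessions lose their MODD value, but those sessions held no day-to-day difference to measure.
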